### **9.2.2. Method of Detecting AEs and SAEs**

- The method of recording, evaluating, and assessing causality of AEs and SAEs and the procedures for completing and transmitting SAE reports are provided in [Appendix 3](#).

- Care will be taken not to introduce bias when detecting AE and/or SAE. Open-ended and non-leading verbal questioning of the participant is the preferred method to inquire about AE occurrence.

### **9.2.3. Follow-up of AEs and SAEs**

After the initial AE/SAE report, the investigator is required to proactively follow each participant at subsequent visits/contacts. All SAEs, and non-serious AEs of special interest (namely stomach erosion, adrenal insufficiency or renal impairment as defined under the stopping and withdrawal criteria above), will be followed until the event is resolved, stabilized, otherwise explained, or the participant is lost to follow-up (as defined in Section 8.3). Further information on follow-up procedures is given in [Appendix 3](#).

### **9.2.4. Regulatory Reporting Requirements for SAEs**

- Prompt notification by the investigator to the sponsor of a SAE is essential so that legal obligations and ethical responsibilities towards the safety of participants and the safety of a study treatment under clinical investigation are met.
- The sponsor has a legal responsibility to notify both the local regulatory authority and other regulatory agencies about the safety of a study treatment under clinical investigation. The sponsor will comply with country-specific regulatory requirements relating to safety reporting to the regulatory authority, Institutional Review Boards (IRB)/Independent Ethics Committees (IEC), and investigators.
- Investigator safety reports must be prepared for suspected unexpected serious adverse reactions (SUSAR) according to local regulatory requirements and sponsor policy and forwarded to investigators as necessary.
- An investigator who receives an investigator safety report describing a SAE or other specific safety information e.g., summary or listing of SAE) from the sponsor will review and then file it along with the Investigator's Brochure and will notify the IRB/IEC, if appropriate according to local requirements.

### **9.2.5. Pregnancy**

- Details of all pregnancies in female participants and, if indicated, female partners of male participants will be collected after the start of study treatment and until the final follow-up visit.
- If a pregnancy is reported, the investigator should inform GSK within 24 hours of learning of the pregnancy and should follow the procedures outlined in [Appendix 4](#).
- Abnormal pregnancy outcomes (e.g., spontaneous abortion, fetal death, stillbirth, congenital anomalies, ectopic pregnancy) are considered SAE.

### **9.3. Treatment of Overdose**

GSK does not recommend specific treatment for an overdose. The investigator will use clinical judgement to treat an overdose as and when they are made aware of this.

In the event of an overdose, the investigator or treating physician should:

1. Contact the Medical Monitor immediately.
2. Closely monitor the participant for AE/SAE and laboratory abnormalities until GSK3186899 can no longer be detected systemically (at least 2 days).
3. Obtain a plasma sample for PK analysis if requested by the Medical Monitor (determined on a case-by-case basis).
4. Document the quantity of the excess dose as well as the duration of the overdosing in the CRF.

Decisions regarding dose interruptions or modifications will be made by the investigator in consultation with the Medical Monitor based on the clinical evaluation of the participant.

### **9.4. Pharmacokinetics**

#### **9.4.1. Blood Sample Collection**

- Plasma samples of approximately 1 mL (from 2 mL of blood) will be collected for measurement of plasma concentrations of GSK3186899 as specified in the SoA. Plasma samples of approximately 2.5 mL (from 5 mL of blood) will be collected from time-points 12 hours and 24 hours post-dose in Part A.
- Instructions for the collection and handling of biological samples will be provided in the SRM. The actual date and time (24-hour clock time) of each sample will be recorded.
- Samples collected for analyses of GSK3186899 plasma concentration may also be used to evaluate safety or efficacy aspects related to concerns arising during or after the study.
- Once the plasma has been analyzed for GSK3186899 any remaining plasma may be analyzed for other compound-related metabolites and the results reported under a separate protocol.

Drug concentration information that may unblind the study will not be reported to investigative sites or blinded personnel until the study has been unblinded.

#### **9.4.2. Urine Sample Collection**

- Urine samples for analysis of GSK3186899 and its metabolites, or for safety biomarkers will be collected at the time-points listed in the SOA. The timing of urine samples may be altered and/or samples may be obtained at additional time points to ensure thorough PK and/or safety monitoring.

- Details of urine sample processing, storage and shipping procedures are provided in the SRM.

#### **9.4.3. Enterotest: Bile Sample Collection**

Bile samples will be collected on Day 1 for the analysis of GSK3186899 and any metabolites for participants in Part A Cohort 3 only.

Bile fluid is recovered on a highly absorbent nylon line which is contained within a weighted gelatin capsule. The 140cm line unwinds after capsule swallowing, the capsule dissolves in the stomach and the line then passes into the duodenum. During withdrawal, the weighted section of the capsule separates from the line and passes in the stool. Additional details of the bile Enterotest sample collection, processing, storage and shipping procedures will be provided in the SRM.

#### **9.5. Pharmacodynamics**

Pharmacodynamic parameters are not evaluated in this study.

#### **9.6. Genetics**

Genetics are not evaluated in this study.

#### **9.7. Pharmacological Biomarkers**

Biomarkers are not evaluated in this study.

#### **9.8. Health Economics / Medical Resource Utilization and Health Economics**

Health Economics/Medical Resource Utilization and Health Economics parameters are not evaluated in this study.

### **10. STATISTICAL CONSIDERATIONS**

Statistical analyses will be performed by, or under the direct auspices of, Biostatistics, GlaxoSmithKline.

Reporting of study data will be performed in accordance with applicable GSK and/or contract research organization (CRO) standards.

Complete details of the planned statistical analyses will be provided in the Reporting and Analysis Plan (RAP).

#### **10.1. Statistical Hypotheses**

The focus of this FTIH study, both single and repeat dose phases, is to evaluate the safety, tolerability and PK of GSK3186899. As such no formal statistical hypotheses will be tested.

Where appropriate, an estimation approach will be taken, and point estimates and confidence intervals (CIs) will be constructed.

## 10.2. Sample Size Determination

The planned sample size is up to 30 subjects for Part A of this study (8 subjects each for Cohorts 1-2 and up to 14 subjects for Cohort 3) and up to 24 subjects for Part B (8 subjects per cohort). Additional subjects may be recruited as replacement for withdrawn subjects.

No statistical techniques were used to calculate the sample size for all cohorts except Part A Cohort 3, which was calculated based on the precision estimate for fed versus fasted and considering feasibility.

The objective of Part A Cohort 3 is to determine if GSK3186899 has a food effect and to inform the dosing regimen for Part B. A precision estimate was therefore used to determine the sample size, based on assumed within subject coefficients of variation (CVw) for AUC and Cmax (20% and 30% respectively). A maximum of 14 subjects will be recruited with the aim of getting evaluable data from 12 subjects. If the estimates for the CVw decrease following review of the data from Cohorts 1 and 2, then less subjects may be recruited, with the aim of obtaining as few as 10 evaluable subjects. The number of planned evaluable subjects will not be less than 10, nor will the number of recruited subjects be greater than 14.

Assuming a point estimate for (fed versus fasted) of 1 (i.e. no food effect), under the variability assumptions described above, and a sample of 12 evaluable subjects, the precision estimates and 90% confidence intervals (CI) for AUC and Cmax are:

Parameter	CVw	Sample size	Precision estimate	90% CI
AUC	20%	12	16%	(0.84, 1.19)
Cmax	30%	12	24%	(0.76, 1.32)

## 10.3. Sample Size Sensitivity

For the assumed variability of AUC and Cmax respectively, the impact of different numbers of evaluable subjects on the precision estimates and 90% confidence intervals were assessed. Results are presented in [Table 6](#).

**Table 6      Sample size sensitivity for fixed within subject coefficient of variation**

Parameter	CVw	Sample size (n)	Point estimate (PE) fed vs fasted	Precision Estimate	90% CI of PE
AUC	20%	6	1	26%	(0.74, 1.35)
		8	1	21%	(0.79, 1.27)
		10	1	18%	(0.82, 1.22)
		12	1	16%	(0.84, 1.19)
		14	1	14%	(0.86, 1.16)
Cmax	30%	6	1	41%	(0.59, 1.69)*
		8	1	32%	(0.68, 1.47)
		10	1	27%	(0.73, 1.37)
		12	1	24%	(0.76, 1.32)
		14	1	22%	(0.78, 1.28)

\* Based on a CVw of 30%, it is estimated that for a sample size of 6 subjects, the lower bound of the 90% CI will be within approximately 41% of the point estimate and the upper bound of the CI within 68%, i.e. assuming a point estimate of 1 (i.e. no difference) the CI would be as wide as (0.59, 1.69).

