## 5.2. Number of Participants

A sufficient number of participants will be screened to ensure that a planned minimum of 54 are eligible to be randomized (Part A: 8 participants into each of Cohorts 1-2 and up to 14 participants for Cohort 3; Part B: 8 participants into each of Cohorts 4-6). A participant is considered evaluable if they complete both screening and at least one treatment period in Part A, or the 10-day treatment period in Part B. Participants that take part in Part A of the study cannot participate in Part B.

If participants prematurely discontinue the study, then additional replacement participants may be recruited and assigned to the same treatment sequence, at the discretion of the Sponsor in consultation with the Principal Investigator, in both Parts A and B.

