	
to assess attainment of steady state.
 
To estimate the extent of accumulation after repeat dosing, the observed accumulation ratio for AUC (<math>(\text{RAUC}_{(0-\text{tau})})</math>), <math>C_{\max}</math> (<math>\text{RC}_{\max}</math>) and <math>C_{\text{tau}}</math> (<math>\text{RC}_{\text{tau}}</math>) may be determined.
 
Statistical analyses of the pharmacokinetic parameter data will be the responsibility of Biostatistics, GlaxoSmithKline. No formal hypotheses will be tested. Pharmacokinetic data will be presented in graphical and/or tabular form and will be summarized descriptively. Full details on the statistical aspects will be detailed in the Reporting and Analysis Plan (RAP).
 
Food Effect (SAD part)
 
The effect of food on the pharmacokinetics of GSK3186899 will be examined. <math>AUC(0-t)</math>, <math>AUC(0-\infty)</math> and <math>C_{\max}</math> of GSK3186899 will be analyzed after a <math>\log_e</math>-transformation of the data. An analysis of variance model will be fitted along with 90% confidence intervals using a mixed effects model, with fed/fasted condition as a fixed effect and subject as a random effect. Point estimates and corresponding 90% confidence intervals will be constructed for the comparisons of interest of GSK3186899 fed – GSK3186899 fasted, using the residual variance. These will then be back-transformed to provide point estimates and corresponding 90% confidence intervals for the geometric mean ratios fed: fasted.
 
Dose Proportionality (SAD and MAD parts)
 
Dose proportionality will be assessed following single doses of GSK3186899 (SAD part) via analyses of <math>AUC(0-\infty)</math> and <math>C_{\max}</math>.
 
Dose proportionality following repeated dosing (MAD part) will be assessed using <math>AUC(0-\text{tau})</math>, <math>C_{\max}</math> and <math>C_{\text{tau}}</math>.
 
A statistical analysis will be performed using the power model. The analysis will be performed on <math>\log_e</math>-transformed data. For each of these parameters a mixed effects model will be fitted with <math>\log_e</math> (dose) as a fixed effect and individual subject fitted as random effects. Estimates of the mean slopes of <math>\log_e</math> (dose) will be reported along with corresponding 90% confidence intervals (slope <math>\approx 1</math> implies dose proportionality).
 
Accumulation (MAD part)
 
The extent of accumulation of GSK3186899 will be based on AUC (<math>\text{RAUC}_{(0-\text{tau})}</math>), <math>C_{\max}</math> (<math>\text{RC}_{\max}</math>) and <math>C_{\text{tau}}</math> (<math>\text{RC}_{\text{tau}}</math>).
 
The focus of the statistical analysis will be to estimate the accumulation ratio, <math>R_o</math>, on the pharmacokinetics of GSK3186899. Following <math>\log_e</math>-transformation, <math>AUC(0-\text{tau})</math> on Day 1 and <math>AUC(0-\text{tau})</math> on the day of last dose will be analysed by a mixed

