8.2.5.1. Statistical Methodology Specification

The following statistical analyses will only be performed if sufficient data is available (i.e. if subjects have well defined plasma profiles).

Pharmacokinetic analysis will be the responsibility of the Clinical Pharmacology Modelling and Simulation Department, (CPMS) and Statistical analyses of the pharmacokinetic parameters will be the responsibility of the Biostatistics Department.

(1) Statistical analysis for comparison of food effect – Single dose study part	
Endpoint / Variables	
 • AUC (0-t) • AUC(0-∞) • Cmax
Model Specification	
 • Log_e-transformed data will be statistically analysed using a Mixed model. • The mixed model will contain 
 ○ Fixed effect: fed or fasted status, period and their interaction term (if tested as significant) ○ Random effect: subject • Only data of subjects participating in Cohort 3 will be included in this analysis, all other dose level data from Cohorts 1 and 2 will be excluded from this analysis. • The Kenward and Roger method for approximating the denominator degrees of freedom and correcting for bias in the estimated variance-covariance of the fixed effects will be used. • An unstructured type of the covariance matrices R (accounting for the within subject variability) and G (accounting for the between subject variability) will be used. • Based on the intercurrent events observed in the study, appropriate strategies from Table 3 in Section 8.2.4 will be considered for handling of missing data (if any) and interpretation of food effect analysis results. If multiple intercurrent events are observed (for e.g., if the

subject does not take the full treatment as well he withdraws study consent), then the data will be handled using more than one strategy as described in Table 3 and interpretations of the results will be made accordingly.
Model Checking & Diagnostics

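### Every 90% confidence interval in the food-effect precision tables (protocol 10.2 and Table 6) is too wide, because the distance to the upper limit was used as the distance to the lower limit

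*Protocol*

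**What the plan says.** Protocol section 10.2 states that Cohort 3 is the only cohort whose size was calculated statistically. It used a precision estimate, together with feasibility, and was "based on assumed within subject coefficients of variation (CVw) for AUC" and Cmax of 20% and 30%. The base case is "Assuming a point estimate for (fed versus fasted) of 1 (i.e. no food effect") with 12 evaluable subjects. It gives a precision of 16% and a 90% CI of (0.84, 1.19) for AUC, and 24% and (0.76, 1.32) for Cmax.

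In section 10.3, "the impact of different numbers of evaluable subjects on the precision estimates and 90% confidence intervals were assessed" for n = 6, 8, 10, 12 and 14 (Table 6). The footnote explains how to read the table, using Cmax at n = 6: the "lower bound of the 90% CI will be within approximately 41% of the point estimate and the upper bound of the CI within 68" per cent, so that "the CI would be as wide as (0.59, 1.69").

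Neither section names the model or degrees of freedom behind the table. Protocol section 10.5.2 specifies the food-effect analysis on the log scale, "with fed/fasted condition as a fixed effect and subject as a random effect". SAP section 8.2.5.1 adds period: "Fixed effect: fed or fasted status, period and their interaction term (if tested as significant").

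**The concern.** With a point estimate of 1 and a log-scale analysis, the 90% CI is symmetric on the log scale, running from exp(-h) to exp(h). The upper limit is then always further from 1, in percentage terms, than the lower limit. The footnote assigns 41% to the lower side. If 41% is really the upper-side distance, every interval built from that column is too wide.

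At stake is the only statistical sample-size justification in the study. Section 10.2 also allows as few as 10 evaluable subjects if the CVw estimates from Cohorts 1 and 2 fall, so Table 6 is the natural place to weigh 10 against 12. A table that overstates interval width misstates that trade-off, and a reader cannot reproduce it from the stated inputs.

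**Working it through.** **Inputs.** CVw 20% (AUC) and 30% (Cmax), point estimate 1, two-sided 90% CI, n = 6 to 14 (protocol 10.2, 10.3 and Table 6). Two-period crossover (protocol 5.1). Log-scale mixed model without period (protocol 10.5.2), so df = n-1.

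**Formulas.**
- sw = sqrt(ln(1 + CVw²)): sqrt(ln 1.04) = 0.1980 for AUC; sqrt(ln 1.09) = 0.2936 for Cmax.
- h = t(0.95, df) × sw × sqrt(2/n).
- 90% CI = exp(-h) to exp(h).

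**Step 1: reproduce the precision column.** Cmax, n = 12: h = 1.7959 × 0.2936 × 0.4082 = 0.2152, and exp(h) - 1 = 0.240, the printed 24%. Cmax, n = 6: h = 2.0150 × 0.2936 × 0.5774 = 0.3415, and exp(h) - 1 = 0.407, the printed 41%. All ten rows match (table below). The column is therefore the distance from 1 to the **upper** limit.

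**Step 2: reproduce the printed intervals.** Write P for the rounded precision. The pair (1 - P, 1/(1 - P)) gives all ten printed CIs to two decimals. Cmax, n = 12: 1 - 0.24 = 0.76 and 1/0.76 = 1.32. Cmax, n = 6: 1 - 0.41 = 0.59 and 1/0.59 = 1.69. The upper-side distance has been used on the lower side and then inverted.

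**Step 3: correct intervals (df n-1).**

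| Parameter | n | exp(h) - 1 | Printed P | Printed CI | Correct CI | Printed/correct log width |
|---|---|---|---|---|---|---|
| AUC | 6 | 0.259 | 26% | (0.74, 1.35) | (0.79, 1.26) | 1.30 |
| AUC | 8 | 0.206 | 21% | (0.79, 1.27) | (0.83, 1.21) | 1.27 |
| AUC | 10 | 0.176 | 18% | (0.82, 1.22) | (0.85, 1.18) | 1.22 |
| AUC | 12 | 0.156 | 16% | (0.84, 1.19) | (0.86, 1.16) | 1.20 |
| AUC | 14 | 0.142 | 14% | (0.86, 1.16) | (0.88, 1.14) | 1.13 |
| Cmax | 6 | 0.407 | 41% | (0.59, 1.69) | (0.71, 1.41) | 1.54 |
| Cmax | 8 | 0.321 | 32% | (0.68, 1.47) | (0.76, 1.32) | 1.39 |
| Cmax | 10 | 0.272 | 27% | (0.73, 1.37) | (0.79, 1.27) | 1.31 |
| Cmax | 12 | 0.240 | 24% | (0.76, 1.32) | (0.81, 1.24) | 1.28 |
| Cmax | 14 | 0.217 | 22% | (0.78, 1.28) | (0.82, 1.22) | 1.26 |

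**Step 4: other explanations.**
- *SAP model with period (df n-2, complete pairs).* No printed CI is recovered; all ten remain 12% to 46% too wide. Four precision values also stop matching (AUC n = 6; Cmax n = 6, 8 and 10).
- *95% intervals.* With df n-1, two AUC rows (n = 10 and 12) coincide, but no Cmax row does: n = 6 would be (0.65, 1.55) and n = 12 (0.77, 1.30). Using the CV directly as the log SD at 95% matches four of ten at best.
- *Normal quantiles or df 2n-2, at 90%.* No row matches.
- *An assurance margin of 50% to 95% on the 90% CI.* At best three of ten match.
- *One higher confidence level.* The implied confidence of the printed limits runs from 93.5% to 97.4% (df n-1), so no single level fits.

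**Step 5: scale.** For the printed n = 12 intervals to be right, CVw would have to be about 24% for AUC and 39% for Cmax. At the stated CVw they are what 8 to 9 complete pairs give: AUC n = 9 is (0.84, 1.19) and Cmax n = 8 is (0.76, 1.32).

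**The case against.** The strongest reply is that nothing depends on the error. It is conservative, no precision criterion is stated and so none is missed, no hypothesis is tested (protocol 10.1), and the SAP's food-effect method does not use Table 6. Section 10.2 also cites feasibility, and section 5.4 says the exact size will follow the variability seen in Cohorts 1 and 2. All of this is true. It limits the consequence but does not make the figures right.

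The 54% figure comes from n = 6, and section 10.2 rules out planning for fewer than 10 evaluable subjects. That is fair. Over n = 10 to 14 the excess is 13% to 22% for AUC and 26% to 31% for Cmax, and the largest shift in any limit is 0.10 (Cmax n = 10, upper limit 1.37 against 1.27).

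The n-2 alternative holds only if both fed/fasted orders are used. Protocol 7.3.1 and the treatment assignment in SAP 2.3 support that, but protocol 5.6.2 and SAP Figure 1 show fasted first, then fed. If everyone followed that order, period and food could not be separated and the n-2 interval would not exist. This qualifies the alternative, not the main correction.

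The footnote's 68% against a printed limit of 1.69 looks like truncation (unrounded, 68.7%) and is trivial.

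**Conclusion.** The concern holds. All ten CIs in Table 6, both CIs in section 10.2 and the footnote are miscalculated, always on the wide side. At n = 12 the log-scale excess is 20% for AUC and 28% for Cmax; across the table it is 13% to 54%. Matching ten of ten rows at both steps identifies the mechanism.

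The correct 10-subject intervals at the assumed CVw, AUC (0.85, 1.18) and Cmax (0.79, 1.27), are narrower than those printed for 12. The table therefore understates what 10 subjects would deliver.

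The corrected figures assume complete fed/fasted pairs, the stated CVw, a point estimate of 1 and the protocol model (df n-1). Moving to df n-2 changes six of the ten rows at two decimals, by at most 0.03. This is a correction to the stated justification, not to the design, and the final food-effect CI will come from the observed data.

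**What to change.** 1. Replace the CIs in Table 6 and section 10.2 with exp(-h) to exp(h), using the df n-1 values above for the protocol model.
2. Reword the footnote for Cmax, n = 6: lower limit about 29% below 1, upper limit about 41% above, CI (0.71, 1.41).
3. Label the precision column as the distance from 1 to the upper limit, and state the model and degrees of freedom.
4. If the table is to follow the SAP model with period, and both orders are used, take df n-2 instead. For n = 6, 8, 10, 12, 14 that gives AUC (0.78, 1.28), (0.82, 1.21), (0.85, 1.18), (0.86, 1.16), (0.88, 1.14) and Cmax (0.70, 1.44), (0.75, 1.33), (0.78, 1.28), (0.80, 1.24), (0.82, 1.22). The footnote becomes 30% below and 44% above. Recompute the precision column too (for Cmax, 44% at n = 6, 33% at n = 8, 28% at n = 10).
5. A separate, minor point: n in this formula counts complete pairs, whereas protocol 5.2 says "A participant is considered evaluable if they complete both screening and at least one treatment period in Part A". For Cohort 3, define evaluable as having AUC and Cmax from both periods.

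The cost is a table, a footnote and some wording. The planned number of subjects need not change.

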#### 10.4.      Populations for Analyses

For purposes of analysis, the following populations are defined:

Population	Description
Screened	
 
All participants who were screened for eligibility
 

Enrolled	
 
All participants who passed screening and entered the study. Included are: Randomized Participants
 
 
Note: screening failures (who never passed screening even if rescreened) and participants screened but never enrolled into the study (Reserve, Not Used) are excluded from the Enrolled population as they did not enter the study.

Safety	
 
All randomized participants who received at least one dose of study treatment.
 
This population will be based on the treatment the subject actually received.
 
 
Note: Participants who were not randomized but received at least one dose of study treatment should be listed.

PK	
 
All participants in the Safety population who had at least 1 non-missing PK assessment (Non-quantifiable [NQ] values will be considered as non-missing values).
 

